2.5.2. Concomitant Medication Start/End Date

In case of partially missing dates, the imputation will be done as follows.

- If the date is completely missing, no imputation will be performed.
- Otherwise, the following rules will be applied to impute partially missing dates (start date, stop date). If only the day is missing, the 15th day of the month will be used. If both the day and month are missing, the 30th of June will be used.

If the medication was taken prior to study start, and the imputed start date is after first dose date, further adjust the imputed start date as the day prior to first dose date; if the medication was taken after study start, and the imputed start date is prior to first dose date, further adjust the imputed start date as first dose date. Also adjust the imputed medication end date so that it is on or after first dose date.

2.6. Other General Definitions

2.6.1. Measurable Multiple Myeloma and Measurable Type

Measurable disease at baseline is defined by any of the following:

- Serum monoclonal paraprotein (M-protein) level ≥ 1.0 g/dL or urine M-protein level ≥ 200 mg/24 hours; or
- IgA multiple myeloma: Serum M-protein level greater than or equal to 0.5 g/dL or urine M-protein level ≥ 200 mg/24 hours; or
- Light chain multiple myeloma: Serum immunoglobulin free light chain (FLC) $\geq 10 \text{ mg/dL}$ and abnormal serum immunoglobulin kappa lambda free light chain ratio.

If a patient meets criteria for serum M-protein, the measurable disease type is serum; otherwise, if a patient meets criteria for urine M-protein, the measurable disease type is urine; otherwise if a patient meets criteria for FLC, the measurable disease type is FLC.

2.6.2. Type of Multiple Myeloma

Type of myeloma for a patient is determined by serum heavy chain or serum/urinary FLC. Serum heavy chain refers to serum immunoglobulin of IgG, IgA, IgM, IgD, or IgE. Serum/urinary FLC refer to kappa or lambda type.

A patient will be classified as IgG type of myeloma if any reported result contains serum heavy chain 'IgG' regardless of FLC reported. Similarly for IgA, IgM, IgD and IgE type. A patient will

be classified as the light chain type of myeloma if any reported result is either 'Lambda light chains' or 'Kappa light chains' but without heavy chain reported. A patient will be classified as 'Serum free light chain only' if all reported results are 'Not Detected'. A patient will be reported as 'biclonal' if the distinct test results contain different heavy chain values or different FLC values.

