9.2.3.2. Serum Immunoglobulin A, M, and G (M-component)

A blood sample will be drawn for quantitation of M-component by serum protein electrophoresis at visits as indicated in Table 1 and Table 2. Subsequent Ig identification will be done by immunofixation. If the M-component is IgD or IgE, these Ig types should be included in the analysis. A second aliquot of serum shall be stored and analyzed as needed, if daratumumab interference is suspected in the post-treatment serum immunofixation assay.

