2. GENERAL ANALYSIS DEFINITIONS

2.1. Visit Windows

The baseline value is defined as the closest non-missing value taken on or prior to the first dosing date (including time if time is available).

Study day is defined as date of assessment – first dosing date + 1 for any assessment done on or after first dosing date; otherwise, study day is defined as date of assessment – first dosing date.

Day 1 is the first dosing date.

Unless otherwise specified, data to be analyzed or presented over time will be presented by cycle, day, and time point (as appropriate) that are recorded in the eCRF.

However, assessment performed in the same cycle may not be well aligned in time scale for different subjects due to possible cycle delays. To address this, the following by-week windowing rule will be used.

Time Interval	Time Interval	
(Week)	(Study Day)	Target Time Point
Baseline	Day ≤ 1	1
Week 1	$2 \le \text{Day} \le 11$	8
Week 2	$12 \le \text{Day} \le 18$	15
Week 3	$19 \le \text{Day} \le 25$	22
Week 4	$26 \le \text{Day} \le 32$	29
Week 5	$33 \le \text{Day} \le 39$	36
Week 6	$40 \le \text{Day} \le 46$	43
Week 7	$47 \le \text{Day} \le 53$	50
Week 8	$54 \le \text{Day} \le 63$	57
Week 10	$64 \le \text{Day} \le 77$	71
Week 12	$78 \le \text{Day} \le 91$	85
Week 14	$92 \le \text{Day} \le 105$	99
Week 16	$106 \le \text{Day} \le 119$	113
Week 18	$120 \le \text{Day} \le 133$	127
Week 20	$134 \le \text{Day} \le 147$	141
Week 22	$148 \le \text{Day} \le 161$	155

Week 24 Week 28 Week 32 Week 36	$162 \le Day \le 182$ $183 \le Day \le 210$ $211 \le Day \le 238$ $239 \le Day \le 266$	169 197 225 253
 Week 4*(X-1)	$(X-1)*28 - 13$ $\leq Day \leq$ (X-1)*28 + 14	(X-1)*28 + 1

If more than 1 assessment falls within the same time window, the one closest to the target day will be considered as scheduled and others as unscheduled #1, #2, etc., achieving 1 assessment per time interval.

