2.4. Definition of Subgroups

Not applicable for Phase 1.

For Phase 2, exploratory subgroup analyses may be performed for selected efficacy endpoints:

Subgroup	Category	Analysis Type
Age	$18 - < 65, 65 - < 75, \ge 75$	E,S
Sex	Female, Male	E,S
Race	White, Other (excluding unreported)	Е
ISS staging	I, II, III	Е
Number of prior lines of		Е
therapy	1 line, 2-3 lines, >3 lines	
Refractory to PI	Yes	Е
Refractory to last line of prior		
therapy	Yes	E
Prior exposure to lenalidomide	Yes, No	Е
Type of myeloma	IgG vs. non-IgG	Е
	Creatinine clearance: $<30, 30 - <60, \ge 60$	
Renal function	mL/min	E
Bone marrow % plasma cells	≤30, 30<- ≤60, >60	Е

E: efficacy (ORR); S: safety (TEAE)

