2.6.3. ISS Staging

International Staging System (ISS) staging is based on the combination of serum β 2-microglobulin (B2MG) and serum albumin (ALB) at baseline.

- Stage I: B2MG < 3.5 mg/L and ALB $\ge 3.5 \text{ g/dL}$ ($\ge 35 \text{ g/L}$)
- Stage III: B2MG \geq 5.5 mg/L
- Stage II: neither I nor III.

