4. SUBJECT INFORMATION

4.1. Demographics and Baseline Characteristics

Subject eligibility will be summarized for all subjects with a non-missing informed consent date. Number of subjects who did not meet all inclusion/exclusion criteria will be summarized, together with the specific non-met criterion. A listing of subjects who didn't meet all inclusion/exclusion criteria will be produced.

Patient enrollment will be summarized by country and site.

The following demographic and baseline characteristic panels will be summarized by dose group (2, 4, 8, or 16 mg/kg) and overall for Phase 1, and for the safety population for Phase 2:

- Demographics: age (continuous), age category (18 to < 65 years, 65 to < 75 years, and ≥ 75 years), sex (male, female), race (White, Black, Asian, Other, Not reported), ethnicity (Hispanic or Latino, Not Hispanic or Latino, Not reported), height (cm), weight (kg), baseline ECOG performance status (0, 1, 2).
- Baseline disease characteristics: type of myeloma (IgA, IgD, IgE, IgG, IgM, light chain, biclonal, other), ISS Staging (I, II, III), time since initial MM diagnosis (years), number of lytic bone lesions (None, 1-3, 4-10 more than 10), and bone marrow % plasma cells < 5, ≥5 − ≤ 10, >10 − ≤ 30, > 30).
- Disease related laboratory values: hemoglobin (g/L), hemoglobin category (< 80 g/L, 80 − 100 g/L, >100 g/L), platelets (giga/L), platelets category (< 75 giga/L, ≥ 75 giga/L), calcium (mmol/L), calcium category (>ULN, ≤ULN), corrected calcium (mmol/L), corrected calcium category ((>ULN, ≤ULN), creatinine (umol/L), creatinine category (> ULN, ≤ ULN), (mg/L), creatinine clearance (mL/min), creatinine clearance category (≥ 90, 60 < 90, 30 < 60, 15 < 30, < 15 mg/L), albumin (g/L), and albumin category (< 35 g/L, ≥ 35 g/L).

- Renal impairment using baseline creatinine clearance: Stage 1: ≥ 90 ml/min; Stage 2: 60 90 mL/min; Stage 3: 30 <60 mL/min; Stage 4: 15 <30 mL/min; Stage 5: < 15 mL/min

In addition, two panels of baseline laboratory tests will be summarized: hematology and serum chemistry.

The frequencies of CTC toxicity grade for these laboratory parameters at baseline will also be provided.

General medical history (including past and current conditions) will be summarized separately by body system and preferred term. Listing will be generated for abnormal medical history and prior surgeries.

Vital signs, including temperature, pulse, systolic and diastolic blood pressure at baseline will be summarized

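### SAP 2.6.2 types myeloma from any result at any time, with no order between the IgG and biclonal rules, so an on-treatment daratumumab band can change a subject's type

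*SAP*

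**What the plan says.** SAP 2.6.2 assigns IgG type on this rule: "A patient will be classified as IgG type of myeloma if any reported result contains serum heavy chain 'IgG' regardless of FLC reported". The same rule is extended to IgA, IgM, IgD and IgE. Light-chain type requires a kappa or lambda result with no heavy chain reported, and the serum-free-light-chain-only category requires every result to be 'Not Detected'. The section also says: "A patient will be reported as 'biclonal' if the distinct test results contain different heavy chain values or different FLC values". None of these rules names a time point, and no order among them is given.

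The neighbouring definitions do name one. SAP 2.6.1 defines measurable disease at baseline, and SAP 2.6.3 bases ISS stage on serum beta-2 microglobulin and "serum albumin (ALB) at baseline".

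The derived type is used in two main places. SAP 4.1 tabulates it under "Baseline disease characteristics: type of myeloma (IgA, IgD, IgE, IgG, IgM, light chain, biclonal, other". SAP 2.4 makes IgG versus non-IgG a Phase 2 ORR subgroup, under the statement that "exploratory subgroup analyses may be performed for selected efficacy endpoints"; SAP 5.2 words the same subgroup analyses as ones that will be done.

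On the assay, Protocol 9.2.3.2 has immunoglobulin type identified by immunofixation and keeps a second serum aliquot for use "if daratumumab interference is suspected in the post-treatment serum immunofixation assay". Footnote o to Protocol Table 2 repeats that provision. The CR definition in SAP 5.2 allows for the interference; SAP 2.6.2 does not.

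**The concern.** Disease type is a fixed characteristic that should be known before treatment. The Protocol introduction describes daratumumab as an IgG1-kappa antibody, so if its band is reported on a post-dose immunofixation, the record contains an IgG heavy chain and a kappa light chain that do not come from the myeloma. A rule that accepts any result then lets the study drug alter the subject's recorded type.

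Two outputs are exposed. The baseline table would mix disease type with drug artefact. The ORR subgroup would be defined partly by post-treatment data, which undermines a comparison of response between its levels. SAP Section 3 says the data cut is meant to support a BLA submission, so these tables have readers beyond the study team.

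**Working it through.** The plan states no figure to reproduce here. The check applies the SAP 2.6.2 rules to each possible pre-dose type, adds one on-treatment IgG-kappa result, and reads off the type under each possible order of the rules.

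**Inputs**
- Typing rules: SAP 2.6.2.
- Added result (IgG heavy chain, kappa light chain): daratumumab isotype, Protocol Section 1.
- Repeated sampling: Protocol Table 2 schedules serum M-component at screening, Cycle 1 Visits 2 and 4, Cycle 2 Visit 1, Visit 1 of later cycles, follow-up and end of trial.

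**Result of adding an IgG-kappa band**

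| Pre-dose type | Biclonal overrides | IgG rule first |
|---|---|---|
| IgG kappa | IgG | IgG |
| IgG lambda | biclonal | IgG |
| IgA, IgM, IgD or IgE (kappa or lambda) | biclonal | IgG |
| Light chain, kappa | IgG | IgG |
| Light chain, lambda | biclonal | IgG |
| Not Detected | IgG | IgG |

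If only results on or before the first dose are used, no row changes under either order.

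**How many could move (illustration only)**

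Assume 30 Phase 2 subjects (SAP 1.4) and the isotype mix in Protocol 1.1.1, about 50% IgG and 20% IgA. That gives 30 × 0.50 = 15 IgG, 30 × 0.20 = 6 IgA, and 30 − 21 = 9 others. Assume further that all 9 others are light chain, that a share k between 0.50 and 0.67 of subjects is kappa (not in the documents), and that every subject has a reported drug band. The counts below are therefore upper bounds.

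Biclonal overrides:
- Entering IgG = 9k: 4.5 at k = 0.50; 5.4 at 0.60; 6.0 at 0.67.
- Leaving IgG for biclonal = 15(1 − k): 7.5 at k = 0.50; 6.0 at 0.60; 5.0 at 0.67.
- Net change in IgG = 9k − 15(1 − k) = 24k − 15: −3.0 at k = 0.50; −0.6 at 0.60; +1.1 at 0.67. It is zero at k = 15/24 = 0.625.

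IgG rule first:
- Entering IgG: 6 + 9 = 15. Leaving: 0.

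Whether the IgG group grows or shrinks thus depends on a precedence the SAP does not state and a kappa share the documents do not give.

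**Measurable-disease type**

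SAP 2.6.1 sets a serum limit of 0.5 g/dL for IgA disease and 1.0 g/dL otherwise. Protocol 4.2 admits subjects with serum M-component of at least 1.0 g/dL and/or urine of at least 200 mg/24 h. If 2.6.1 takes IgA status from 2.6.2, losing that status matters only for an IgA subject with serum 0.5 to <1.0 g/dL who qualified by urine. That subject moves from serum to urine type, which changes the value shown in the SAP 5.4.1 waterfall plot. No other eligible subject is affected.

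**The case against.** The strongest reply is that a baseline reading is already intended. SAP 4.1 calls type of myeloma a baseline characteristic, and SAP 2.1 says: "The baseline value is defined as the closest non-missing value taken on or prior to the first dosing date". The words in 2.6.2 could simply mean any of the serum and urine results used for typing. As evidence of intent this stands. It does not settle the derivation: 2.1 picks one closest value, whereas 2.6.2 pools results, and a programmer cannot follow both as written. A table heading does not supply the missing date limit.

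A second reply is that biclonal must override, because any subject with two heavy chains meets two heavy-chain rules and the biclonal clause could otherwise never operate. That is the more sensible reading. It narrows movement into IgG to kappa light-chain and 'Not Detected' subjects, but it also takes IgG-lambda subjects out, so misclassification remains.

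Third, the protocol's language on interference is conditional, and nothing shows that a drug band would be entered as the subject's heavy chain. This stands: the frequency is unknown.

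A reader might go further and infer that the rule shifts responders into IgG, because they stay on drug longer, and so creates a subgroup difference. Take 15 IgG and 15 non-IgG subjects with 75% ORR in both, and move 30% of non-IgG responders and 10% of non-IgG non-responders. IgG then reads (11.25 + 3.375)/(15 + 3.375 + 0.375) = 14.625/18.75 = 78%, and non-IgG 7.875/11.25 = 70%. The documents do not support that inference. The 30% and 10% are assumed, and the whole gap comes from their difference: at any equal rate r, (11.25 + 11.25r)/(15 + 15r) stays at 75%. The example also needs the IgG rule to come first. Non-responders, too, are sampled on drug by Cycle 1 Visit 4 and Cycle 2 Visit 1, after weekly dosing has begun.

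**Conclusion.** The point holds as a defect in the derivation rule. SAP 2.6.2 has no pre-dose limit and no order of precedence. With an IgG1-kappa study drug and repeated immunofixation, following it literally can misclassify disease type, in either direction if biclonal overrides. This rests on a drug band being reported for at least some subjects, which the protocol foresees but does not quantify.

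The documents do not determine the net direction or size of bias in the IgG versus non-IgG subgroup. The stakes are limited: a baseline table, one exploratory ORR subgroup, and possibly the waterfall value of a narrow group of IgA subjects. The SAP plans no formal test (5.1.1). The primary endpoint (adverse events) and overall ORR do not use the variable. Subgroup precision is poor in any case: 11 responders of 15 has an exact 95% interval of roughly 45% to 92%. The change is still worth making, because it removes a known artefact from a variable presented as baseline.

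**What to change.** In SAP 2.6.2, limit every typing rule (heavy chain, light chain, serum free light chain only, biclonal) to results from samples taken on or before the first dose, using the SAP 2.1 baseline convention, including time where available. State that biclonal takes precedence when pre-dose results show different heavy chains or different light chains. SAP 2.4 can say at the same time whether a biclonal subject counts as non-IgG.

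The cost is two or three sentences and a date filter in the derivation. Screening serum and urine immunofixation are already collected, so no new data are needed.

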2.6.3. ISS Staging

International Staging System (ISS) staging is based on the combination of serum β 2-microglobulin (B2MG) and serum albumin (ALB) at baseline.

- Stage I: B2MG < 3.5 mg/L and ALB $\ge 3.5 \text{ g/dL}$ ($\ge 35 \text{ g/L}$)
- Stage III: B2MG \geq 5.5 mg/L
- Stage II: neither I nor III.

2.6.4. Refractory Disease

Refractory myeloma is defined as disease that is nonresponsive while on salvage therapy, or progresses within 60 days of last therapy in patients who have achieved minimal response (MR) or better before progressing. The following refractory disease categories are derived: refractory to PI only, refractory to IMiD only, refractory to PI + IMiD, refractory to the last line of prior therapy, refractory to alkylating agents (ALKY), or refractory to PI + IMiD + ALKY, In addition, refractoriness to bortezomib, carfilzomib, lenalidomide, pomalidomide, thalidomide or combinations will also be derived.

2.6.5. Month and Year

One year equals to 365.25 days. One month equals to 365.25/12 days.

2.6.6. Years since Initial Multiple Myeloma Diagnosis

This is calculated as date of first dose – date of initial MM diagnosis +1, divided by 365.25.

2.6.7. Total Dose Received

Total dose of daratumumab is the sum of administered doses recorded on the infusion forms at all visits, which is calculated in mg/kg.

2.6.8. Duration of Treatment/Infusion

Duration of study drug in months is derived as last dose date – first dose date + 1, divided by 365.25/12, separately for daratumumab, lenalidomide and dexamethasone.

Duration of daratumumab infusion in hours is derived for each infusion. It includes actual infusion time and interruption time if any.

2.6.9. Duration of Follow-up

The end of follow-up is the date of death for subjects who died; for subjects who are still alive, the end of follow-up is defined as the maximum date of the following study evaluations: labs (hematology, chemistry, immunology), adverse events, vital signs, ECOG performance status,

bone marrow cytogenetics, lytic bone lesions, extra-medullary plasmacytomas, study drug administration, ECG, disposition, concomitant medications, subsequent therapy, clinical events/disease response per investigator and date of last known to be alive.

Duration of follow-up (in months) equals the end of follow-up minus the first dosing date plus 1, divided by 365.25/12.

2.6.10. Relative Dose Intensity

The relative dose intensity (%) is the ratio of total dose received (mg/kg) and total planned dose (mg/kg), calculated as the planned dose level times the number of administered infusions.

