3. STUDY DESIGN AND RATIONALE

3.1. Overview of Study Design

This is an open-label, multicenter Phase 1/2 safety study of daratumumab in combination with Len/Dex in the treatment of subjects with relapsed or relapsed and refractory multiple myeloma. The dose escalation portion of the study (Phase 1) will be a standard 3 + 3 design and will evaluate daratumumab, at doses from 2 mg/kg up to a maximum of 16 mg/kg, in combination with Len/Dex in 28-day treatment cycles. The standard "3 + 3" rules for dose escalation will be applied, However, if the study sites have identified 4 eligible subjects to start a new dose level, all 4 subjects may be enrolled. The MTD will be defined as the highest dose of the combination regimen at which less than 33% of subject's experience DLT. A recommended Phase 2 dose (RP2D) will be determined during Phase 1. The MTD or any dose evaluated in the range of 2 to 16 mg/kg of daratumumab may be considered as the RP2D based on available safety,

50

PK/pharmacodynamic, and efficacy data from Phase 1. The RP2D could be selected before escalation to or completion of the 16 mg/kg cohort. Once the RP2D is determined, the expansion (Phase 2) will open to further explore the safety and efficacy of the RP2D in approximately 30 subjects.

For Phase 1 and Phase 2 of the study there will be a Screening Period followed by the first 2 treatment cycles and will consist of weekly daratumumab infusions, totaling 4 infusions during each 28-day cycle. Cycles 3 through 6 will consist of daratumumab infusions administered every other week; Cycle 7 and all subsequent cycles will consist of monthly daratumumab infusions. The combination treatment may continue until the subject experiences disease progression or unacceptable toxicity, whichever comes first. For Phase 1 only, to minimize the risk of cytokine release syndrome, the first infusion of the first cycle will be preceded by a predose infusion the day before the scheduled full-dose infusion. The predose infusion will be 10% of the full dose, but will never be more than 10 mg in total dose. Further measures to prevent cytokine release syndrome will include premedication with antihistamines, acetaminophen, and dexamethasone before each daratumumab infusion (both predose and full dose).

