6. DOSAGE AND ADMINISTRATION

The start of a cycle is defined as the start of any of the study treatments (ie, daratumumab or Len/Dex). If all treatments are held, then it should be reported as a cycle delay.

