6.4. Delaying or Skipping Treatment

After completion of each cycle, initiation of a new cycle should be delayed for at least 1 week if the subject experiences toxicity. A subject whose cycle is delayed should be evaluated weekly for resolution or recovery of the toxicity, and a decision regarding further delay or initiation of

Key: CrCl = creatinine clearance.

Estimated by CrCl as calculated by the Cockcroft-Gault, Diet in Renal Disease (MDRD), or Chronic Kidney Disease Epidemiology Collaboration (CKD-EPI) formulas formula (Attachment 7).

the next cycle should be made. However, the start of a new cycle after more than a 3-week delay (with all study therapy withheld) may occur only if there is clear clinical benefit and only after approval by the sponsor.

Refer to Section 6.6.1 for details on management of infusion-related reactions. **ONLY if any of the following criteria below are met, and the event cannot be ascribed to lenalidomide, the daratumumab infusion must be held to allow for recovery from toxicity**. The following parameters must be met on the first day of a new cycle (after Cycle 1):

- Platelet count $\geq 50 \times 10^9/L$
- Febrile neutropenia of any grade
- Neutropenia with infection, of any grade
- Hemoglobin $\geq 8.0 \text{ g/dL}$ ($\geq 4.96 \text{ mmol/L}$) (prior red blood cell transfusion or recombinant human erythropoietin use is allowed)
- ANC $\ge 0.75 \times 10^9 / L$
- Nonhematologic toxicity of Grade 3 or higher must have recovered to baseline or Grade 1 or less unless otherwise specified

A subject whose cycle is delayed should be evaluated at least weekly for resolution of the toxicity. For severe hematologic toxicity (Grade 3 or higher), a complete blood count may be repeated more frequently as necessary until the requirements for reinitiating treatment are met.

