4.4. Extent of Exposure

Descriptive statistics will be provided by dose group and overall for total number of pre-dose (Phase 1 only) and full daratumumab infusions, treatment duration (the interval between date of first infusion and date of last infusion), total dose (mg) received from pre-dose and full infusions, and relative dose intensity (calculated for each full-infusion as the ratio of dose intensity (mg/kg) and the planned dose level (mg/kg)).

The number and percent of patients with incomplete daratumumab infusions (i.e. total volume of infusion not administered) and reason for incomplete infusion will be summarized by dose group, visit and overall.

The duration of daratumumab infusions (hours) will also be summarized.

All infusions will be listed by patient and visit. For Phase 1, both pre-dose and full infusions will be listed.

Exposure to lenalidomide and dexamethasone (dose and duration) will be also summarized separately by dose group, visit and overall.

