6.1.1. Treatment Emergent Adverse Events

The following summaries will be provided for all TEAEs:

- An overview of TEAE will be provided, including the incidence of TEAE, serious TEAE, maximal severity of TEAE, treatment discontinuation due to TEAE, TEAE leading to treatment interruption, and death due to TEAE.
- An overview of TEAE by subgroups specified in Section 2.4
- Separate listings for each category above.

In addition, the following summaries will be generated:

- TEAEs by system organ class (SOC) and preferred term (PT)
- Most common (at least 5%) TEAEs by system organ class (SOC) and preferred term (PT)
- TEAEs by SOC, PT, and grade 3 or 4.
- TEAEs by SOC, PT, and worst toxicity grade
- TEAEs by SOC, PT, and relationship to study medication
- Most common (at least 10%) TEAEs by system organ class (SOC), preferred term (PT), and grade 3 or 4.
- TEAEs by SOC, PT, and grade 3/4 by subgroups specified in Section 2.4
- Serious TEAEs by SOC and PT
- Serious TEAEs by SOC, PT, and worst toxicity grade
- Serious TEAEs by SOC, PT, and relationship to study medication
- Most common (at least 1%) serious TEAEs by system organ class (SOC) and preferred term (PT)
- Grade 3 or 4 TEAEs by SOC and PT
- Grade 3 or 4 TEAEs by SOC, PT, and relationship to study drug

The following summaries for TEAEs leading to treatment modifications will be provided:

- TEAEs leading to infusion interrupted by PT, and relationship to study drug
- TEAEs leading to infusion prolonged by PT, and relationship to study drug.
- TEAE leading to hospitalization or prolonged hospitalization by SOC and PT.
- Treatment discontinuation due to TEAEs by PT and relationship to study drug
- Study discontinuation due to TEAEs by PT and relationship to study drug
- Death due to TEAEs by PT and relationship to study drug.

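### Daratumumab relative dose intensity is divided by infusions given, so it shows how complete those infusions were and cannot register an infusion never given

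*SAP*

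**What the plan says.** SAP 2.6.10 defines relative dose intensity as dose received over planned dose, both in mg/kg, with the planned dose "calculated as the planned dose level times the number of administered infusions". The numerator comes from SAP 2.6.7: "Total dose of daratumumab is the sum of administered doses recorded on the infusion forms at all visits".

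SAP 4.4 describes the statistic a second time, as "calculated for each full-infusion as the ratio of dose intensity (mg/kg) and the planned dose level (mg/kg"), without defining dose intensity. It lists total dose separately, as "total dose (mg) received from pre-dose and full infusions". SAP 4.3, on treatment compliance, only points to 4.4.

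SAP 4.4 also plans summaries of the number of infusions, treatment duration, and incomplete infusions with their reasons, plus a listing of every infusion for each subject at each visit. SAP 6.1.1 adds "TEAE leading to treatment interruption" to the adverse event overview.

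On the protocol side, section 6.1 fixes the infusion schedule. Section 6.4 provides that, when its criteria are met and "the event cannot be ascribed to lenalidomide, the daratumumab infusion must be held to allow for recovery from toxicity". Section 6 states: "The start of a cycle is defined as the start of any of the study treatments". A cycle can therefore begin with lenalidomide or dexamethasone alone.

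**The concern.** Relative dose intensity is normally read as the share of the intended dose that the subject received. Here the term called total planned dose is rebuilt from what was given, so the ratio falls only when a given infusion was incomplete or below the planned level. Omitted infusions leave no trace in it.

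The primary objective is the safety profile, and SAP section 3 says that the data cut is meant to support a licence application. This is the only planned ratio of received to planned daratumumab dose. A reader who sees a value near 100% may conclude that adverse event incidence was observed at close to scheduled exposure. The statistic as defined cannot support that conclusion.

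**Working it through.** The documents state no value of relative dose intensity, so there is no figure of the plan's own to reproduce. The check is algebra plus the protocol schedule.

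**Inputs (Protocol 6.1), full-dose infusions.** Cycles 1 and 2: 4 each. Cycles 3 to 6: 2 each. Cycle 7 onward: 1 each.
- Through Cycle 6: 4 + 4 + 2 × 4 = 16.
- Through Cycle 13: 16 + 7 = 23, over 13 × 28 = 364 days.

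**Assumptions.** The numbers of missed infusions are illustrative. Infusions given are complete unless stated. The Phase 1 predose is left out. Doses in mg/kg use the weight from which the dose was calculated.

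**Formulas.** Let L be the planned level, d the dose given at each infusion, g the number given and s the number scheduled.
- SAP 2.6.10: sum of d / (L × g).
- Against schedule: sum of d / (L × s).

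If every given infusion is complete, the sum of d is L × g. The SAP ratio is then 100% whatever s is, and the schedule-based ratio is g/s.

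| Never given | SAP ratio | Of 16 scheduled | Of 23 scheduled |
|---|---|---|---|
| 1 | 100% | 15/16 = 93.8% | 22/23 = 95.7% |
| 2 | 100% | 14/16 = 87.5% | 21/23 = 91.3% |
| 4 | 100% | 12/16 = 75.0% | 19/23 = 82.6% |

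**The form in SAP 4.4.** The mean over a subject's full infusions of d/L equals the sum of d / (L × g). For a subject on a constant level this is the 2.6.10 ratio, so it has the same blind spot.

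**Ordering of subjects.** A subject given all 16, one of them half-given, shows 15.5/16 = 96.9%. That is below the 100% of a subject who missed four. If the subject who missed four also had one half-given infusion, the SAP ratio is 11.5/12 = 95.8%, against 11.5/16 = 71.9% of schedule.

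**Can the planned group summaries stand in?** Only roughly, because infusions become less frequent over time. Take two subjects with nothing missed:
- One receives the 8 infusions of Cycles 1 and 2, the last on Day 50.
- The other receives the 23 of Cycles 1 to 13, the last on Day 337.
- Means: (8 + 23)/2 = 15.5 infusions and (50 + 337)/2 = 193.5 days.
- Scheduled by Day 193: 8 + 8 + 1 (Day 169) = 17.
- The means suggest 15.5/17 = 91.2%, although no infusion was omitted.

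**Delay.** Suppose each of Cycles 2 to 13 starts one week late. The last infusion moves from Day 337 to Day 337 + 12 × 7 = 421. The SAP ratio and a cycle-based schedule ratio (23/23) both stay at 100%.

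**The case against.** The strongest reply is that nothing is hidden. SAP 4.4 lists every infusion for each subject and tabulates incomplete infusions with reasons. With a fixed schedule and 42 to 58 subjects (Protocol 11.2), missing infusions can be read off one subject at a time. The SAP also states its denominator openly. This stands, and it rules out a reading that a reader might be tempted to make: that omissions could not be found in the reported data. What remains is that no summary compares infusions given with infusions scheduled, and that the label total planned dose describes something else.

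Three further inferences are not supported.

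- *That 2.6.10 and 4.4 conflict.* They agree for a subject on a constant level. They can differ only if the level changes or infusions are pooled across subjects.
- *That the Phase 1 predose distorts the ratio.* SAP 4.4 ties the ratio to full infusions, which largely excludes it. An explicit statement is still worthwhile, because 2.6.7 sums over all visits and the predose is small: "The predose infusion will be 10% of the full dose, but will never be more than 10 mg in total dose". If it were counted in both terms, an assumed 70 kg subject at 16 mg/kg given all 16 full infusions would show (16 × 1120 + 10)/(17 × 1120) = 94.2%.
- *That the protocol directs infusions to be skipped.* In Protocol 6.4 only the heading mentions skipping; the text describes holding and delay. Omission remains possible because another component can start the cycle.

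It is also fair to say that a schedule-based ratio remains blind to cycle delay, and that the documents do not show that a daratumumab-specific discontinuation date is collected. Both points shape the fix.

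**Conclusion.** The point holds as a low-severity correction to a descriptive exposure statistic. Under either SAP wording the ratio describes the completeness of infusions given and is unaffected by infusions never given. In the illustration, four of 16 omitted gives 100% where the schedule gives 75.0%. The result is algebraic; only its size depends on the assumed number missed, for which the documents give no rate.

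A reader might go further and infer that adverse events were in fact observed below scheduled exposure, or that a reported result is biased. The documents support neither. No test, power figure or endpoint estimate uses this ratio.

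**What to change.** Use one subject-level definition in SAP 2.6.10 and 4.4:

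- Total planned dose is the subject's assigned dose level times the full-dose infusions scheduled by Protocol 6.1 in cycles started, up to daratumumab discontinuation or data cutoff, whichever comes first.
- If no daratumumab-specific discontinuation date is collected, end at the last daratumumab dose date (available through SAP 2.6.8) and state that omissions after it are not counted.
- Exclude the Phase 1 predose from both terms.
- State which planned level applies to a subject who continues at a lower level after a dose-limiting toxicity (Protocol 6.5).
- Report infusions given beside infusions scheduled.
- Summarise the number and length of cycle delays separately, since this ratio does not capture them.

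At minimum, relabel the present ratio *percent of planned dose per administered infusion* and add the given-versus-scheduled count.

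The cost is SAP wording and a small derivation from infusion records, cycle start dates and the chosen end date. The reported intensity may be less favourable; the documents do not show by how much.
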